### **3.1.6. Allocation to Interventional Group**

Stratified randomization will be performed based on severity category (severe versus severe complicated) in a 2:1 fashion (two to the FMT intervention (PMT-001, 002, or 003) and one to the standard of care control group). The randomization schedule will be prepared using a random-size block strategy to ensure balance throughout the trial. Prior to enrollment of the first subject, a randomization table will be produced for each category using Stata statistical software and the “Ralloc” package.

[figure not shown]
If subjects are known to have enteral access (either actively receiving capsule medications and/or nutrition by mouth or via pre-existing enteric tube, as prescribed by the clinical care team), they will undergo a second randomization in a 1:1 fashion between allocation to FMT by enema (i.e., PMT-001) or FMT by upper enteral administration (i.e., PMT-002 or PMT-003). Subjects who are randomized to FMT but who lack enteral access or who are deemed to have ileus (i.e., enteral medications and nutrition held) by the clinical care team will receive PMT-001 enema. Subjects who are randomized to FMT but have bowel discontinuity will only be eligible for the intervention arm that coincides with their presumed side of CDI (e.g. if CDI in residual rectum/colon, only eligible for PMT-001). Prior to enrollment of the first subject, a randomization table will be produced for the second (route of administration) randomization using R statistical software.

Subjects randomized to receive FMT, and then to receive FMT via upper delivery will have the decision made between PMT-002/PMT-003 according to how other medications and nutrition are being delivered (i.e., those receiving nutrition and medications via enteric tube will receive PMT-002 suspension, and those eating food and receiving oral medications will receive PMT-003 capsules). Cross-over between PMT-002 and PMT-003 will be permitted if repeat FMT administration is indicated, but a subject’s mode of nutrition and medication administration has changed. Cross-over between PMT-001 and PMT-002/003 will be permitted if repeat FMT administration is indicated, but a subject has lost enteral access and is unable to tolerate oral medications.

For a graphical representation of the allocation to the interventional groups, refer to [Figure 1](#).

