## **2. Study Objectives**

### **2.1. Primary Objective**

To evaluate the efficacy of fecal microbiota transplantation (FMT) performed using the Penn Microbiome Therapy (PMT) suite of products to treat subjects with severe and severe-complicated/fulminant *Clostridium difficile* infection (S/SC/F-CDI) by comparing the clinical outcomes of three treatment strategies: (1) no investigational product (standard of care only); (2) upper gastrointestinal administration FMT in addition to standard of care; (3) lower gastrointestinal FMT in addition to standard of care.

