#### **4.5. Total Number of Subjects and Sites**

Recruitment will be performed at one site with six participating PennMedicine University of Pennsylvania Health System locations: (1) the Hospital of the University of Pennsylvania (HUP), (2) Penn-Presbyterian Medical Center (PPMC), (3) Pennsylvania Hospital (PAH), (4) Lancaster General Hospital (LGH), (5) Chester County Hospital (CCH), and (6) PennMedicine Princeton Medical Center (PMPMC). Enrollment targets 90 subjects, with 30 randomized to each arm.

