#### **6.1.4. Enteral Access Check**

The enrolled subject's enteral access will be reviewed to determine whether the subject qualifies for randomization between upper and lower gastrointestinal delivery of investigational product.

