### **8.5.5. Exploratory Analyses**

To characterize (1) the baseline gut bacterial community composition and host immune phenotype associated with S/SC/F-CDI, we will apply 16S ribosomal RNA (rRNA) gene sequencing to initial (pre-FMT) stool specimens, Luminex bead assay (cytokine/chemokine levels) and flow cytometric analysis (granulocyte/mononuclear cell counts) to serum and blood specimens collected as part of routine clinical care prior to FMT. To characterize (2) the change in gut bacterial community composition and host immune phenotype associated with each of the above treatment strategies, we will apply the same assays to post-FMT stool, peri-rectal, and serum/blood specimens. To determine (3) the relationship between baseline gut bacterial community composition, host immune phenotype, and treatment outcome in patients with S/SC/F-CDI, we will perform regression modeling with bacterial community composition, cytokine/chemokine levels, and granulocyte/mononuclear cell counts as predictor variables.

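### As-allocated comparisons of upper FMT, enema FMT and control are confounded by gut function, because FMT subjects who cannot take the upper route go to enema while their counterparts in control are not separated out

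*Combined protocol and SAP*

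**What the plan says.** All references are to the combined protocol and SAP.

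- **Objective.** Section 2.1 evaluates efficacy "by comparing the clinical outcomes of three treatment strategies": control, upper FMT and lower FMT. Sections 2.3 and 8.5.5 go on to characterize the change in gut bacteria and "host immune phenotype associated with each of the above treatment strategies".
- **First randomization (3.1.6).** "Stratified randomization will be performed based on severity category (severe versus severe complicated"), and allocation is "in a 2:1 fashion (two to the FMT intervention (PMT-001, 002, or 003) and one to the standard of care control group"). Enteral access is not a stratification factor.
- **Second randomization (3.1.6).** This applies only to FMT subjects with known enteral access: "they will undergo a second randomization in a 1:1 fashion between allocation to FMT by enema" or by the upper route.
- **No route randomization (3.1.6).** "Subjects who are randomized to FMT but who lack enteral access or who are deemed to have ileus" receive enema. Here ileus means a care-team judgement with enteral medication and nutrition held. Bowel discontinuity also fixes the route, according to the presumed side of the infection.
- **Enteral access check (6.1.4).** "The enrolled subject's enteral access will be reviewed to determine whether the subject qualifies for randomization between upper and lower gastrointestinal delivery". It comes before randomization (6.1.5), and Table 3 lists it under screening and enrollment. Nothing says that the result is kept for control subjects or used in analysis.
- **Planned efficacy analysis (8.5.2).** FMT in aggregate against no FMT, one-sided 0.2. No route comparison is specified.

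**The concern.** The 2:1 randomization makes pooled FMT comparable with control. It does not make either route arm comparable with control, because a baseline characteristic decides who can enter the upper arm and who is sent to enema. That characteristic is gut function, which is plausibly prognostic: in Table 2 ileus places a subject in the severe-complicated category, and under Section 3.2.1 documented ileus blocks in-hospital resolution until it is noted as resolved.

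If route-ineligible subjects recover more slowly, a table of the three strategies as allocated would tend to flatter the upper route and penalise enema even with no effect of FMT or of route. A reader could take this for a route effect, on the very question that Section 2.1 poses. Gut function could plausibly also affect the stool and immune measures reported by strategy, although nothing below quantifies that.

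**Working it through.** **Inputs.** From the plan: 90 subjects, with "Enrollment targets 90 subjects, with 30 randomized to each arm" (4.5); 2:1 and then 1:1 allocation (3.1.6); durations of 4 and 7 days (8.4). Assumed: f, the share without enteral access or with ileus and enteral intake held, taken as 10 to 30%. Bowel discontinuity is left out of f and would add to the problem.

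**The plan's power figures.** Power = Φ(√(d·a(1−a))·|ln r| − 1.2816), with d = 90 events, a = 1/3 and two-sided 0.2.
- 4 to 2 days: √20 × 0.693 − 1.282 = 1.82, giving 0.965 (stated 0.97).
- 7 to 4 days: √20 × 0.560 − 1.282 = 1.22, giving 0.889 (stated 0.90).

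These concern pooled FMT v control and are not in dispute.

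**Arm composition.** Of 60 FMT subjects, 60f go straight to enema and 60(1−f) split 1:1.
- Upper: 30(1−f) subjects, route-ineligible share 0.
- Enema: 30(1−f) + 60f = 30(1+f) subjects, share 60f / 30(1+f) = 2f/(1+f).
- Control: 30 subjects, share f.
- Pooled FMT: share 60f/60 = f, the same as control.

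| f | Upper n, share | Enema n, share | Control n, share |
|---|---|---|---|
| 10% | 27, 0% | 33, 18% | 30, 10% |
| 20% | 24, 0% | 36, 33% | 30, 20% |
| 30% | 21, 0% | 39, 46% | 30, 30% |

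Thirty per arm is expected only if f = 0.

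**Severity strata.** The same algebra holds inside each stratum with its own f. Fever, lactate, hypotension or SIRS criteria also place a subject in severe-complicated (Table 2), so access varies within that stratum. Stratification by severity therefore does not remove the imbalance.

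**Illustrative bias.** Assume no FMT effect and mean times of 4 days (route-eligible) and 7 days (route-ineligible). Bias = 3 days × difference in share.

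| f | Upper v control | Enema v control | Upper v enema |
|---|---|---|---|
| 10% | −0.3 | +0.25 | −0.55 |
| 20% | −0.6 | +0.40 | −1.0 |
| 30% | −0.9 | +0.48 | −1.4 |

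**Simulation.** Settings: exponential times, no FMT effect, route-ineligible subjects taking 1.5 to 3 times as long, f of 10 to 50%, 3,000 trials per setting, log-rank test at one-sided 0.2.
- Pooled FMT v control rejected in 18 to 20% of trials, essentially nominal.
- With all three arms restricted to route-eligible subjects, upper v control rejected in 20 to 22% and upper v enema in 19 to 22%. The restriction removes the bias.

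**The case against.** **No planned test is distorted.** The only efficacy test is pooled FMT against control. The one-sided 0.2 threshold is stated for that test alone, safety is only described, and Section 8.5.5 names no between-strategy test. This stands. A reader might infer that the trial's type I error is inflated, or that every comparison is confounded. The documents support neither: the 2:1 randomization protects the pooled comparison, and among route-eligible subjects all three strategies are randomized.

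**Access may already be known for controls.** The check precedes randomization and is not limited to FMT subjects. This also stands. What is missing is any statement that the result is recorded for controls and used. Because the trial is open label, classifying controls afterwards would be open to bias. Figure 1 could not be read here, so the absence of a split rests on the text.

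**The prognostic link is weaker than it looks.** Table 2 and Section 3.2.1 rely on ileus or dilation wording in notes and radiology reports. The route rule needs care-team ileus with enteral intake held. A subject can meet the wording and still be fed enterally, and a subject can lack access without ileus. So slower recovery in the route-ineligible group is likely but not shown.

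**The size is assumed.** Section 8.4 gives 4 and 7 days as alternative whole-trial scenarios, not as subgroups. Even on that split, 4,000 simulated trials per setting had upper ahead of control on mean days in 60, 70 and 76% of trials at f = 10, 20 and 30%, against 50% by chance. The bias of 0.3 to 0.9 days is below the trial-to-trial standard deviation of that difference (1.1 to 1.3 days). It would be wrong to say that upper will look better; the results tilt that way. The simulations also leave out severity stratification and competing events.

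**Conclusion.** The point holds for as-allocated comparisons by strategy: upper v control, enema v control and upper v enema. The imbalance in route-ineligible subjects (0, f and 2f/(1+f)) follows from the allocation rule and needs no assumption beyond f above zero. Its direction, favouring upper and penalising enema, rests on slower recovery in route-ineligible subjects. Its size depends on f and on the difference in recovery, neither of which the plan gives. The tabulated bias is an illustration of scale and applies to time to resolution only.

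The primary analysis needs no correction. The gap is that the three-strategy objective and the by-strategy characterization have no stated like-for-like comparator, although the design can supply one. It is worth closing because the information is already due to be gathered at enrollment.

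**What to change.** 1. **Section 6.1.4:** fix and record route eligibility (enteral access, no ileus with enteral intake held, no bowel discontinuity) for every enrolled subject, including those later assigned to control, before the 2:1 randomization.
2. **Section 8.5.5, and any efficacy or safety display by strategy:** compare upper, enema and control only among route-eligible subjects in all three arms. List route-ineligible subjects separately and descriptively. At f = 20% there would be about 12 on FMT and 6 in control (6 and 3 at f = 10%), too few for a comparison.
3. **Section 2.1:** state that the primary inference is pooled FMT v control and that by-strategy comparisons are made in the route-eligible subset.

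**Cost.** One sentence in each of the three sections and one case report form field. Treatment, randomization and the primary analysis do not change. By-strategy comparisons lose about a share f of subjects, leaving about 30(1−f) per arm. As a guide only, since no route test is planned: with 60(1−f) events, 1:1 allocation, 4 to 2 days and two-sided 0.2, the power formula above gives 0.92, 0.90, 0.87 and 0.83 for upper v control at f = 0, 10, 20 and 30%.

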**Figure 1: Allocation to Interventional Group Flow Diagram**

### 3.2. Study Endpoints

#### 3.2.1. Primary Study Endpoints

The primary outcome is resolution of symptoms associated with S/SC/F-CDI, listed below. The primary outcome will be satisfied when the subject is discharged from the hospital (not to hospice or palliative care) or, while the subject remains hospitalized, when the following criteria are met for 72 hours:

- If radiology study or studies performed, ileus/dilation/megacolon either not noted or noted as resolved (electronic medical record search words: “ileus”, “dilated”, “dilation”, or “megacolon”)
- Ileus/megacolon either noted as resolved by any provider documentation or not noted (electronic medical record search words: “ileus”, “megacolon”)
- WBC < 15,000 cells/uL
- Serum creatinine decreased, unchanged, or increased by  $\leq 0.2$  mg/dL over 72 hours (if not receiving continuous renal replacement therapy (CRRT) or hemodialysis (HD))
- Lactate  $\leq 2.2$  mmol/L (if measured by clinical care team)
- No vasopressors used (including epinephrine, norepinephrine, phenylephrine, or vasopressin)
- Temperature  $< 38.5$  °C and  $\geq 35.6$  °C
- < 8 bowel movements per day and < 600 mL unformed stool (if volume recorded)
- Meeting fewer than 3 systemic inflammatory response syndrome (SIRS) criteria (i.e., no more than two of the following: heart rate > 90 beats per minute; respiratory rate > 20 breaths per minute or PaCO2 < 32 mmHg; temperature > 38°C or < 36°C; WBC > 12,000 cells/uL, < 4,000 cells/uL, or > 10% immature (band) forms)

Discharge to hospice, need for bowel surgery (colectomy, diverting ileostomy), and death will count as failures. Subjects who undergo bowel surgery after initial PMT administration will not be eligible for additional administrations.

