## **4. Study Population and Duration of Participation**

### **4.1. Inclusion Criteria**

1. One or more episodes of CDI with symptoms including bowel movements altered in frequency or consistency from baseline.
2. Stool test positive for *Clostridium difficile* by EIA by FDA-cleared assay within 7 days prior to enrollment.
3. Age  $\geq$  18 years
4. Meets any one of the listed criteria for severe or severe-complicated/fulminant disease (see [Table 2](#) below) within 72 hours of enrollment.
5. Receiving antibiotic treatment for S/SC/F-CDI per current IDSA guidelines.

Enrollment criteria details:

1. Must either meet  $\geq$ 1 criteria in severe category or in severe complicated category to be enrolled.
2. If the subject meets criteria in both categories, stratify to the higher severity category (severe complicated).
3. Detailed enrollment criteria definitions (for [Table 2](#)):
  - a. WBC  $\geq$ 15,000 cells/uL – if any value in the time period meets this definition.
  - b. Hypotension with systolic blood pressure sustained  $<$  90mmHg for three or more hours or requiring vasopressors (epinephrine, norepinephrine, phenylephrine, or vasopressin).

- c. Acute kidney injury – increase in serum creatinine level by  $\geq 50\%$  or new dialysis initiation.
  - i. If a baseline serum creatinine value is not available, acute kidney injury will be defined as a serum creatinine  $>1.5$  mg/dL.
- d. Temperature  $\geq 38.5$  °C or  $<35.6$  °C - one value needed in time period.
- e. Ileus, bowel dilation or megacolon.
  - i. Ileus: If noted in any provider documentation or problem list (search words “ileus”) OR
  - ii. If the words “dilated” “dilation” or “ileus” are noted in a radiology report on intestines/colon, or if “megacolon” noted.
- f. Lactate  $>2.2$  mmol/L - if any value in the time period meets this definition.
- g. SIRS criteria:
  - i. Heart rate  $> 90$  beats per minute
  - ii. Respiratory rate  $> 20$  breaths per minute or  $\text{PaCO}_2 < 32$  mmHg
  - iii. Temperature  $>38^\circ\text{C}$  or  $<36^\circ\text{C}$
  - iv. WBC  $> 12,000$  cells/uL,  $<4,000$  cells/uL, or  $>10\%$  immature (band) forms

Use Table 2 below to decide if the subject meets criteria for enrollment and their stratification category (severe versus severe-complicated).

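### The in-hospital resolution list omits the blood-pressure and kidney-injury thresholds used at entry, so a subject can count as resolved while still meeting the trial's severe criteria

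*Combined protocol and SAP*

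**What the plan says.** **Entry (Section 4.1 and Table 2).** Hypotension means systolic pressure below "90mmHg for three or more hours or requiring vasopressors (epinephrine, norepinephrine, phenylephrine, or vasopressin"; either half qualifies, and Table 2 classes it as severe-complicated. Kidney injury is defined as "Acute kidney injury – increase in serum creatinine level by" 50% or more, "or new dialysis initiation". Where there is no earlier value, "If a baseline serum creatinine value is not available, acute kidney injury will be defined as a serum creatinine" above 1.5 mg/dL. Table 2 classes kidney injury as severe, and it is one of only two criteria, with WBC, that place a subject in that stratum.

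**Resolution (Section 3.2.1, carried into 7.7 and 8.1).** The outcome is met at discharge other than to hospice or palliative care or, in hospital, when every listed item holds for 72 hours. The haemodynamic item is "No vasopressors used (including epinephrine, norepinephrine, phenylephrine, or vasopressin". The renal item is "Serum creatinine decreased, unchanged, or increased by" no more than 0.2 mg/dL over 72 hours, followed by the bracket "if not receiving continuous renal replacement therapy (CRRT) or hemodialysis (HD".

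**Repeat dosing.** Section 3.1.4 ties eligibility to still meeting the severe or severe-complicated criteria in the prior 24 hours. Sections 3.1.2 and 5.2 tie it to failing the improvement criteria and cite 3.2.1.

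**The concern.** The primary endpoint is presented as resolution of the severe disease that qualified the subject for the trial. If the list can be met while an entry criterion still holds, the event does not mean that for those subjects.

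The clearest case is someone who entered on kidney injury alone. If creatinine is already stable and the stool, SIRS and other items are met, that subject may satisfy the list from randomization. The event time then says little about treatment. Events of this kind in both arms would dilute a real difference.

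The gap also reaches beyond the analysis. Because 3.2.1 is cited for repeat dosing, one subject could be improved under one section and still severe under another.

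**Working it through.** This is mainly a check of definitions. I set each entry criterion against the resolution list and asked whether a subject with only that abnormality, and everything else normal, would be counted as resolved in hospital.

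| Abnormality still present | Entry class | Item in 3.2.1 | Counted as resolved? |
|---|---|---|---|
| WBC 16,000 cells/uL | S | WBC below 15,000 | No |
| Temperature 38.6 °C | SC | below 38.5 and at least 35.6 | No |
| Lactate 3 mmol/L | SC | at most 2.2, if measured | No |
| Ileus | SC | not noted, or resolved | No |
| Three SIRS criteria | SC | fewer than three | No |
| Vasopressor use | SC | none used | No |
| Systolic 85 mmHg, sustained, no vasopressors | SC | none | **Yes** |
| Creatinine flat at 3.0 mg/dL, baseline 1.0 | S | 72-hour change only | **Yes** |
| Newly started haemodialysis | S | creatinine item conditioned on not being on dialysis | **Yes**, on the plain reading |

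S is severe and SC severe-complicated. The patient values are illustrative.

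1. **Blood pressure.** SIRS does not close the gap. Its components are heart rate, respiratory rate or PaCO2, temperature and WBC, and two positive components are allowed. Section 3.2.3.1 cites 3.2.1 in connection with hypotension, but 3.2.1 contains no hypotension criterion.
2. **Creatinine.** In the example, 3.0/1.0 is a 200% rise, against an entry threshold of 50%. The 72-hour change is 3.0 − 3.0 = 0, which is within 0.2, so the item is met.
3. **Dialysis.** The bracket reads as a condition for applying the item, like the brackets on lactate (if measured) and stool volume (if recorded) in the same list. No other item requires freedom from dialysis. The entry term is new initiation, so the overlap is clearest for dialysis started recently. The bracket does not separate new from chronic dialysis.

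**The plan's power figures.** Inputs from Sections 4.5 and 8.4: 90 subjects, 60 FMT against 30 control, type I error 0.2. I assume exponential times and that all 90 have the event. Power = Φ(√(90 × 2/3 × 1/3) × ln HR − z), and √20 = 4.472.

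- 4 to 2 days, HR 2, two-sided (z = 1.282): 4.472 × 0.693 − 1.282 = 1.82, power 0.965 (plan: 0.97).
- 7 to 4 days, HR 1.75, two-sided: 4.472 × 0.560 − 1.282 = 1.22, power 0.889 (plan: 0.90).
- At one-sided 0.2, the test in Section 8.5.2, the values are 0.988 and 0.952.

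**Illustration of dilution.** Assume a fraction f of both arms has an uninformative early event. The documents do not give f. They also do not say whether the event is dated at the start or the end of the 72 hours, so both are shown. Simulated log-rank test, 60 v 30, exponential times, one-sided 0.2, 7 to 4 days; ranges are across independent runs:

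| f | Event at time 0 | Event at day 3 |
|---|---|---|
| 0 | 0.94–0.95 | 0.94–0.95 |
| 10% | 0.90 | 0.92 |
| 20% | 0.85–0.86 | 0.89–0.90 |
| 30% | 0.80–0.82 | 0.87 |

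For 4 to 2 days at f = 20%, power goes from 0.98 to 0.94 (time 0) or 0.96 (day 3).

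**The case against.** **The power loss cannot be charged to this gap.** This stands. Entry looks back 72 hours, and for WBC and lactate a single value suffices. A subject enrolled on WBC 16,000 that has since fallen below 15,000 may also meet the list at once, although WBC is perfectly mirrored. Closing the blood-pressure and renal gaps would leave such subjects untouched. Dating the event at day 3 also roughly halves the loss.

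**No bias is shown.** This stands. The same list applies to both arms. A reader might infer that the gap favours FMT or invalidates the primary result; nothing in the documents supports that.

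**Kidney-injury entrants do not all resolve at randomization.** This stands. A reader might infer that they do, but they must also hold fewer than 8 bowel movements a day, under 600 mL of unformed stool if recorded, no ileus and fewer than three SIRS criteria for 72 hours. Creatinine that is still rising by more than 0.2 mg/dL fails the list.

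**Exact mirroring of the renal criterion may be wrong for an infection endpoint.** This stands in part. The current item can be read as asking whether kidney injury is still progressing. Requiring reversal could stop a subject with lasting dialysis dependence, or with an unrecorded chronically raised creatinine, from ever resolving in hospital after the infection has cleared. That argues against a stricter renal item in the primary definition. It does not explain the missing blood-pressure item.

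**The hypotension gap is narrower than untreated hypotension.** It is hypotension not treated with vasopressors; hypotension managed by other means passes as well.

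**Conclusion.** The concern holds for blood pressure and kidney injury only. The hypotension and plateaued-creatinine gaps follow directly from the text. The dialysis gap rests on reading the bracket as an applicability condition. The opposite reading, that a subject must be off dialysis, is not stated anywhere, so the wording needs settling either way. Discharge still counts as resolution, so the problem is confined to the in-hospital route.

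Its size cannot be computed from the documents. The power figures above are illustrative: they depend on an assumed f and on how the event is dated, and they are not specific to this defect. Under the planned one-sided 0.2 test, none of the illustrated values falls below 0.80. The weight of the point therefore lies in what a reported resolution means, and that does not depend on f. It should be fixed before the analysis; it is not a reason to reject the design.

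**What to change.** For the primary endpoint, in Section 3.2.1 and by reference 7.7 and 8.1:

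1. Add the blood-pressure half of the entry definition: no systolic pressure below 90 mmHg sustained for three or more hours.
2. State whether the CRRT/HD bracket means that the creatinine item is not applicable or not met, and treat newly started and chronic dialysis separately.
3. Keep the current creatinine-change item in the primary definition. Prespecify a sensitivity analysis in which subjects who entered on kidney injury are not counted as resolved in hospital while they still meet 4.1 item 3c, with discharge still counting as resolution.

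Separately, reconcile the repeat-dosing passages (3.1.4 against 3.1.2 and 5.2). Section 6.2.4 refers to the severe criteria but points to 3.2.1, so it belongs in the same check. A change to 3.2.1 made for the endpoint should not alter dosing eligibility by cross-reference. Which dosing rule should apply is outside this review.

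The cost is a few lines of wording and one extra analysis. The trial already uses blood pressure, creatinine and dialysis information from the record to judge entry. Some events will occur slightly later. In the sensitivity analysis, subjects with slow or incomplete renal recovery may resolve only at discharge.
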